9.2.3 Study visits

N/A

9.2.4 Study discontinuation

Boehringer Ingelheim reserves the right to discontinue the study overall or at a particular study site at any time for the following reasons:

1. Violation of Good Pharmacoepidemiology Practice (GPP), the study protocol, or the contract by a study site, investigator or research collaborator, disturbing the appropriate conduct of the study

The investigator/the study site/research collaborator will be reimbursed for reasonable expenses incurred in case of study/site termination (except in case of the third reason).

9.3 VARIABLES

Exposure cohorts

Treatment with empagliflozin (as add-on therapy with metformin)

• Treatment with a sulfonylurea (as add-on therapy with metformin) Exposure will be identified by recorded prescription filling matching the NDC codes for empagliflozin or sulfonylurea, respectively. See list of identifying NDC codes in the additional workbook titled "NDC Codes.xlsx".

Covariates

Covariates included will be those previously published in the literature.

Baseline characteristics	Metformin + Sulfonylureas (N =)	Metformin + Empagliflozin (N =)	St. Diff.
Age; mean (sd)			
Age categories			
18 - 54; n (%)			
55 - 64; n (%)			
65 - 74; n (%)			
>= 75; n (%)			
Male; n (%)			
Race			
White; n (%)			
Black; n (%)			
Asian; n (%)			
Hispanic; n (%)			
North American Native; n (%)			
Other/Unknown; n (%)			
Region			
Northeast; n (%)			
South; n (%)			
Midwest; n (%)			
West; n (%)			
Quarter and year of cohort entry			
Q3 2014; n (%)			
Q4 2014; n (%)			
Q1 2015; n (%)			
Q2 2015; n (%)			
Q3 2015; n (%)			
Combined comorbidity score; mean (sd)			
No. distinct diagnoses; mean (sd)			
Diabetic nephropathy; n (%)			
Diabetic retinopathy; n (%)			
Diabetes with other ophthalmic conditions or ophtalmic procedures; n (%)			
Diabetic neuropathy; n (%)			
Diabetes with peripheral circulatory disorders; n (%)			

001-MCS-90-118_RD-23 (1.0) / Saved on: 25 Nov 2019

Diabetic Foot: n (%)			
Lower extremity amputation: n (%)			
Skin infections: p (%)			
Skill infections, $n(70)$			
Foot ulcer; n (%)			
Erectile dysfunction; n (%)			
Hypoglycemia ; n (%)			
Hyperglycemia; n (%)			
(%)			
Diabetic ketoacidosis; n (%)			
Hyperosmolar hyperglycemic nonketotic syndrome; n (%)			
Diabetes with unspecified complication; n (%)			
Naive new user; n (%)			
Monotherapy; n (%)			
Dual therapy with metformin; n (%)			
Concomitant initiation or current use of metformin; n (%)			
Concomitant initiation or current use of sulfonylureas; n (%)			
Past use of metformin; n (%)			
Past use of sulfonylureas; n (%)			
Past use of insulin; n (%)			
Past use of GLP-1 RAs; n (%)			
Past use of glitazones; n (%)			
Any use of meglitinides; n (%)			
Any use of alpha-glucosidase inhibitors; n (%)			
Lifestyle factors			
Obesity; n (%)			
Overweight; n (%)			
Smoking; n (%)			
Alcohol abuse or dependence; n (%)			
Drug abuse or dependence; n (%)			
Ischemic heart disease; n (%)			
Acute myocardial infarction; n (%)			
Old myocardial infarction; n (%)			
Unstable angina; n (%)			
Stable angina; n (%)			
Other chronic ischemic heart disease; n (%)			
Previous coronary revascularization; n (%)			
Ischemic or hemorrhagic stroke; n (%)			
Ischemic stroke; n (%)			
Transient ischemic attack; n (%)			
	1	1	

Hemorrhagic stroke and other cerebrovascular disease; n $\binom{6}{3}$		
Late effects of cerebrovascular disease or procedure; n		
(%)		
Heart failure; n (%)		
Peripheral arterial disease or surgery; n (%)		
Atrial fibrillation; n (%)		
Other cardiac dysrhythmia; n (%)		
Other cardiovascular disease; n (%)		
Hypertension; n (%)		
Hyperlipidemia ; n (%)		
Edema; n (%)		
Non-diabetic renal dysfunction; n (%)		
Acute kidney injury; n (%)		
Chronic kidney disease; n (%)		
Chronic kidney disease stage 1-2; n (%)		
Chronic kidney disease stage 3+ or dialysis; n (%)		
Hypertensive nephropathy; n (%)		
Miscellaneous renal insufficiency ; n (%)		
Kidney or bladder stones; n (%)		
Urinary tract infections; n (%)		
COPD; n (%)		
Asthma; n (%)		
Obstructive sleep apnea; n (%)		
Pneumonia; n (%)		
Liver disease; n (%)		
Osteoarthritis; n (%)		
Other arthritis, arthropathies and musculoskeletal pain; n (%)		
Dorsopathies; n (%)		
Fractures; n (%)		
Falls; n (%)		
Osteoporosis; n (%)		
Disorders of thyroid gland; n (%)		
Depression; n (%)		
Anxiety; n (%)		
Sleep disorders; n (%)		
Dementia; n (%)		
Delirium; n (%)		
Psychosis; n (%)		
Angiotensin converting enzyme inhibitors; n (%)		
Angiotensin II receptor blockers; n (%)		

Beta-blockers; n (%)		
Calcium-channel blockers; n (%)		
Thiazide diuretics; n (%)		
Loop diuretics; n (%)		
Other diuretics; n (%)		
Nitrates; n (%)		
Other hypertension drugs; n (%)		
Digoxin; n (%)		
Anti-arrhythmics; n (%)		
COPD or asthma medications; n (%)		
Statins; n (%)		
Other lipid-lowering drugs; n (%)		
Antiplatelet agents; n (%)		
Oral anticoagulants; n (%)		
Heparin and other low-molecular weight heparins; n (%)		
Nonsteroidal anti-inflammatory drugs; n (%)		
Oral corticosteroids; n (%)		
Bisphosphonates; n (%)		
Opioids; n (%)		
Antidepressants; n (%)		
Antipsychotics; n (%)		
Anticonvulsants; n (%)		
Benzodiazepines; n (%)		
Other anxiolytics or hypnotics; n (%)		
Dementia medications; n (%)		
Antiparkinsonian medications; n (%)		
Hospitalization within prior 30 days; n (%)		
Hospitalization during prior 31-365 days; n (%)		
No. hospitalizations; mean (sd)		
No. hospital days; mean (sd)		
No. emergency department visits; mean (sd)		
No. office visits; mean (sd)		
Endocrinologist visit within prior 30 days; n (%)		
Endocrinologist visit during prior 31-365 days; n (%)		
No. endocrinologist visits; mean (sd)		
Internal medicine visit within prior 30 days; n (%)		
Internal medicine visit during prior 31-365 days; n (%)		
No. internal medicine visits; mean (sd)		
Cardiologist visit within prior 30 days; n (%)		
Cardiologist visit during prior 31-365 days; n (%)		

No. cardiologist visits; mean (sd)	
Electrocardiogram; n (%)	
No. electrocardiograms, mean (sd)	
No. distinct medication prescriptions; mean (sd)	
Use of glucose test strips; n (%)	
No. HbA1c tests ordered; mean (sd)	
No. glucose tests ordered; mean (sd)	
No. microalbuminuria tests ordered; mean (sd)	
No. creatinine tests ordered; mean (sd)	
No. BUN tests ordered, mean (sd)	
No. lipid tests; mean (sd)	

The table above shows our complete set of baseline characteristics. All comorbidities and previous acute conditions and previous utilization in the previous 12 months will be recorded. Age at index date will be calculated as the time difference between the index date and the patient's birth date. Identification of comorbidities and previous utilization will follow the following rules:

- Chronic comorbidities and previous acute conditions will be identified by occurrence of at least one ICD 9/10 for the respective condition in any position. See the additional workbooks titled "ICD 9 Dx Codes.xlsx" and "ICD 10 Dx Codes.xlsx" for a detailed list of ICD 9/10 codes that identify comorbidities.
- Previous healthcare utilization will be identified by occurrence of CPT or HCPCS codes for the respective form of utilization. See the additional workbooks "CPT codes.xlsx" and "HCSPCS codes.xlsx" for a detailed list of CPT and HCPCS codes.
- Previous prescription medications will be identified by occurrence of prescription filling with a medication's respective NDC or HCSPCS code. See additional workbook "NDC codes.xlsx" and "HCSPCS codes.xlsx" for a detailed list of relevant codes.

Also, given that we are comparing a branded agent against generic agent, we will perform exploratory instrumental variable analysis, in order to account for the confounding by indication. Some example of instrumental variables we can use and will explore the appropriateness of are:

- First three digits of zip code (ZIP3) and/or State
- National Provider Identifier (NPI)
- Index date and/or index quarter

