	The study will analyze the clinical and economic effect of empagliflozin in T2D patients with CVD. Empagliflozin initiators as an add-on therapy to metformin, comprise the treatment population. Patients initiating sulfonylureas as add-on to metformin comprise the control population.

Population:	IQVIA's claims database is composed of more than 190 million unique enrollees from national and sub-national health plans and self-insured employer groups from 2006 to the present. The database is considered representative of the gender and age demographics of the insured United States population.		
	Inclusion criteria:		
	• Prevalent metformin use + initiation of empagliflozin OR prevalent metformin use + initiation of a sulfonylurea		
	• ≥ 18 years of age at index date during study observation		
	• ≥1 inpatient and/or ≥ 2 outpatient claims denoting T2D diagnosis (in any position) in the 12 months prior to index date (Diagnosis codes available in the appendix Error! Reference source not found.)		
	• ≥1 inpatient and/or ≥2 outpatient claims denoting CVD (in any position) diagnosis in the 12 months prior to index date (Diagnosis codes available in the additional workbooks "ICD 9 Dx Codes.xlsx" and "ICD 10 Dx Codes.xlsx")		
	• ≥12 months of no exposure to T2D medications in the pre-index period (excluding metformin in both arms)		
	• ≥ 2 months post-index date		
	• ≥ 12 months of continuous enrollment prior to index date		
	Exclusion criteria:		
	• Diagnosis of Type 1 Diabetes, secondary, or gestational diabetes in the 12 months prior to index date (Diagnosis codes available in the additional workbooks "ICD 9 Dx Codes.xlsx" and "ICD 10 Dx Codes.xlsx"))		
	• Diagnosis of severe comorbidities including malignancy, end-stage renal disease, human immunodeficiency virus, Hepatitis C infection, or organ transplant in the 12 months prior to index date (Diagnosis codes available in the additional workbooks "ICD 9 Dx Codes.xlsx" and "ICD 10 Dx Codes.xlsx")		
	• Admission to nursing home in the 12 months prior to index date		

Variables:	Exposure:		
	 Treatment with Empagliflozin as add-on to 		
	metformin versus Treatment with Sulfonylurea as		
	add-on to metformin		
	Baseline Characteristics (Covariates):		
	• Demographics		
	• E.g. Age, sex, geographic identifier, and time-of-entry indicator		
	 Calendar time of cohort entry (in quarters and days) 		
	 Comorbidities/previous health events 		

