Data analysis:	Propensity scores will be calculated using the listed covariates (below) and used to construct PSM cohorts, if the post-matching sample size still allows for a powered analysis, or IPTW cohorts if not. Using observed clinical events, we will calculate incidence rates and 95% confidence intervals for PSM (or IPTW) cohorts. We will estimate the hazard ratios and confidence intervals via Cox regression for our primary outcome (HHF). We will also estimate differences in healthcare utilization using incident counts, by performing either Poisson or negative binomial regression. Differences in cost outcomes will be assessed by generalized linear regression using a Gamma family link function. We will also explore instrumental variables that are employed to minimize residual confounding after PSM (or IPTW).	
Milestones:	The database for this analysis will be constructed by March 08, 2021, Data analyses will be complete April 12, 20201. A report of the findings from this study will be complete for review June 7, 2021.	

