9.4 DATA SOURCES

This study will utilize IQVIA's Real-World Data (RWD) Adjudicated Claims Database (formerly known as PharMetrics Plus). IQVIA's claims database is composed of more than 190 million unique enrollees from national and sub-national health plans and self-insured employer groups from 2006 to the present.¹⁵ The database is considered representative of the sex and age demographics of the insured United States population.¹⁶ The database contains a multitude of patient data points that are relevant for this study including:

- Demographic, geographic, and insurance type/enrollment information,
- Primary and specialty care visit dates and diagnosis codes,
- Medication use including refill dates, quantity, and days supplied, and
- Hospitalizations and emergency department visit dates, length of stay, and diagnosis codes

We anticipate having access to claims data that was generated though at least December 31, 2019. IQVIA's database has been extensively used in pharmacoepidemiological research. Recent examples include *Pandya et al.* (2020) and *Stolshek et al.* (2018).^{16,17} The claims data will be fully de-identified prior to receiving access for analyses.

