9.9 LIMITATIONS OF THE RESEARCH METHODS

- Inferior level of internal validity compared to prospective study
- Study sample does not represent patient population covered by Medicare, as commercially-insured population is meaningfully different from overall U.S. patient population
- Subject to confounding, i.e. confounding variables may account for treatment with empagliflozin.
- Relevant patient variables (e.g. HbA1c lab values, creatinine lab values, socioeconomic status) are not available
- Necessary to assume accurate recordkeeping/reporting of patient characteristics, treatments, and clinical/economic outcomes

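### Insurance type is available in the data but missing from the declared covariate set, so the branded-versus-generic cost and utilisation comparisons are not adjusted for it

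*Protocol*

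**What the plan says.** - **Data held.** Protocol 9.4 introduces its list of contents with "The database contains a multitude of patient data points that are relevant for this study including", and the first item is "Demographic, geographic, and insurance type/enrollment information".
- **Covariates.** The table in 9.3 covers age, sex, race, region, entry quarter, comorbidities, diabetes drugs, lifestyle, other medication, prior utilisation and test counts. No row concerns insurance, payer or plan. The text after it states: "The table above shows our complete set of baseline characteristics". The abstract's demographic examples are "E.g. Age, sex, geographic identifier, and time-of-entry indicator", again without insurance.
- **Propensity score.** From the abstract: "Propensity scores will be calculated using the listed covariates (below) and used to construct PSM cohorts".
- **Outcome models.** Section 9.7.1, Step 3, names Cox, Poisson or negative binomial, and Gamma log-link models, with no added covariates.
- **Branded versus generic.** Section 9.3 says "given that we are comparing a branded agent against generic agent, we will perform exploratory instrumental variable analysis". The candidate instruments are ZIP3 or state, prescriber identifier, and index date or quarter. Section 9.7.2 makes the model conditional on feasibility.
- **Limitations.** Section 9.9 says "Relevant patient variables (e.g. HbA1c lab values, creatinine lab values, socioeconomic status) are not available". It does not mention insurance type.

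**The concern.** A confounder has to relate both to which drug is started and to the outcome. Insurance type is a plausible candidate on both counts. The protocol itself worries that one drug is branded and the other generic, and coverage is a natural route by which brand status affects what gets filled. The secondary outcomes are costs per patient per month and healthcare use, and the terms of a patient's plan can plausibly affect both. These links are inferences; the protocol does not state them.

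If insurance type differs between the arms after matching or weighting, part of any cost or utilisation difference would reflect plan mix and not the drug. The protocol's quality check would give no warning, because standardised differences are computed only for variables in the table. A larger sample would narrow the interval without removing the bias.

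**Working it through.** No figure in the protocol depends on this point, so there is none to reproduce. The check has two parts.

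**1. Tracing insurance type through the protocol**

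| Place | Role of insurance or enrolment |
|---|---|
| 9.4 | Insurance type and enrolment listed as held and relevant |
| 9.2.2 | Enrolment used for eligibility (12 months before index) |
| 9.1, 9.7.1 | Disenrolment ends follow-up |
| 9.3 table | No insurance row |
| Abstract, data analysis | Propensity score from listed covariates |
| 9.7.1, Step 1 | Balance accepted if standardised differences do not exceed 10% |
| 9.7.1, Step 3 | No insurance term in any model |
| 9.7.2 | Instruments contain no coverage variable |
| 9.9 | Not named as a limitation |

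Enrolment is used; insurance type is not used anywhere.

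**2. Illustrative size (all inputs assumed)**

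Let p1 and p0 be the shares of empagliflozin and sulfonylurea patients in the higher-cost plan type after matching or weighting, and R the ratio of mean cost in that plan type to the rest. With no true drug effect, the observed cost ratio is

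[1 + p1(R − 1)] / [1 + p0(R − 1)].

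With p0 = 0.45:

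| R | p1 = 0.55 | p1 = 0.65 |
|---|---|---|
| 1.2 | 1.11/1.09 = 1.018 | 1.13/1.09 = 1.037 |
| 1.3 | 1.165/1.135 = 1.026 | 1.195/1.135 = 1.053 |

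For a wider range, take p0 = 0.40, p1 from 0.50 to 0.70 and R from 0.7 to 1.5. The extremes are 0.79/0.88 = 0.898 and 1.35/1.20 = 1.125. The direction therefore depends on the assumptions as well.

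The standardised difference for a binary variable is (p1 − p0) / √{[p1(1 − p1) + p0(1 − p0)]/2}:

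- 0.55 v 0.45: 0.10/√0.2475 = 0.20
- 0.65 v 0.45: 0.20/√0.2375 = 0.41

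These are about two and four times the 10% limit. Such imbalances would fail the protocol's own criterion if the variable were tabulated.

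**The case against.** **Selection is the analyst's choice.** Section 9.3 says covariates follow published work, and calling a data item relevant does not promise adjustment for it. A reader might infer that 9.3 and 9.4 contradict each other; they do not. But a rule of following the literature does not supply the missing adjustment or explain why a variable held in the data is left out.

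**The table is not truly final.** The abstract adds length of metformin use, 9.1 adds exposure time, and the table's entry quarters stop at Q3 2015 although indexing runs to 1/31/2020. The final propensity model may therefore differ. This stands and lowers confidence that insurance type would be left out in practice. Still, none of these lists contains it, and an analysis plan that follows the declared set would omit it.

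**Variation may be limited and partly captured.** Section 9.9 describes a commercially insured population, and race, region, entry quarter and prior utilisation may absorb some imbalance. This stands too, and residual bias may be smaller than the illustration. However, 9.4 names national plans, sub-national plans and self-insured employers, so some variation in coverage is likely to remain.

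**Three stronger readings are not supported.**
- That the heart failure hazard ratio is biased. No document links plan type to heart failure admission. A noticeable shift needs a strong assumed association: a rate ratio of 0.60 would be stronger than the 0.65 treatment hazard ratio used in 9.5.
- That insurance type is the best available stand-in for socioeconomic status. Race is tabulated and ZIP3 is a candidate instrument; nothing ranks them.
- That detailed payer, plan or benefit fields are held. Section 9.4 says only insurance type.

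**Conclusion.** The point holds for the secondary cost and utilisation comparisons. The protocol lists insurance type as held and relevant, leaves it out of a covariate set it calls complete, and meets the branded-versus-generic problem only with an exploratory, conditional analysis that contains no coverage variable. Bias is plausible but not demonstrated. Its size cannot be derived from the documents: the illustrated cost ratios of 1.02-1.05, and 0.90-1.13 over the wider inputs, rest wholly on assumed plan shares and cost ratios, and on insurance type being unrelated to the covariates already balanced. For the primary heart failure outcome, an effect is possible but the documents give no basis for asserting one. The change should be made because it is cheap, with moderate confidence that the omission matters.

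**What to change.** - Add insurance type at index, at whatever level of detail the data hold, to the 9.3 table, the propensity score and the standardised-difference check.
- Enter it as a covariate in the cost and utilisation models as well.
- If the field proves unusable, say so and list it in 9.9 as an unmeasured confounder.

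**Cost.** One categorical covariate from a source already planned for use. Sparse categories may need collapsing. If insurance type predicts treatment but not the outcome, overlap or precision may fall slightly. On timing, section 6 places the final analysis plan (06/07/2021) and dataset construction (07/02/2021) after the protocol date of 6/1/2021. The abstract gives earlier dates for database construction and analysis, so the sponsor should confirm which schedule applies.

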9.3.1 Exposures

Exposure cohorts

- Treatment with empagliflozin (as add-on therapy to metformin)
- Treatment with a sulfonylurea (as add-on therapy to metformin)

9.3.2 Outcomes

9.3.2.1 Primary outcomes

Primary outcome

• First hospitalization for congestive heart failure (HHF) (we will first analyze this by looking at diagnosis code in any position, we will then run the analysis considering diagnosis coding in either the principal or secondary position).

The primary scope of the analysis will be limited to the primary outcome (hospitalization for HF), for which the study will be powered for, and limited to HCRU and cost outcomes. For all exploratory effectiveness outcomes outlined above, we will first examine the number of events, and incidence rate of the events in the follow-up for the unmatched cohort, before performing the final analysis, to evaluate feasibility of inclusion of these exploratory outcomes.

Clinical outcomes will be identified by occurrence of a combination of the ICD 9/10 for the respective condition and HCSPCS code. See additional workbooks "ICD 9 Dx Codes.xlsx" and "ICD 10 Dx Codes.xlsx" and "HCPSC codes.xlsx" for a detailed list of relevant ICD 9/10 codes and HCSPCS codes, respectively.

Effectiveness Outcome	Metformin + Sulfonylurea(IR)	Metformin + Empagliflozin (IR)	Hazard Ratio (95% CI)
HHF			
MACE			
Myocardial infarction			
Stroke			
Coronary revascularization			
All-cause death			

See sample results for the propensity score-matched population below:

Utilization Outcome (12 months post index date)	Metformin + Sulfonylurea (IR)	Metformin + Empagliflozin (IR)	Coefficient (95% CI)	P value
Hospitalizations				
LOS				
ED visits				
Outpatient visits				
Drug orders				
Total care costs				
Medical costs				

Pharmacy costs		
2		

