7. RATIONALE AND BACKGROUND

Approximately 13% of adults in the United States have been diagnosed with diabetes, with approximately 90% of those cases attributable to T2D.¹ Patients with diabetes are at much higher risk for CVD than patients without diabetes, and adults with T2D have a 2-to-4 fold higher risk of cardiovascular morbidity and mortality.² The American Heart Association lists T2D as one of the seven major controllable risk factors for CVD, with glycemic control being a contributing factor to cardiac impairments among patients with T2D.²

Empagliflozin (Jardiance), is a SGLT2i; this therapy was first approved in 2014 for the reduction of HbA1c in patients with T2D, and is available both as monotherapy and as add-on therapy. In 2016 empagliflozin received a new indication for reducing cardiovascular death in patients with T2D and CVD, and a 2020 update to the American Diabetes Association Standards of Care recommends the addition of either SGLT2i or GLP1-RA for patients with pre-existing cardiovascular disease or kidney disease.³ In clinical studies, the rate of death in patients taking empagliflozin vs. placebo has been significantly reduced (3.7%, vs. 5.9%; 38% relative risk reduction; p-value <0.001), as have rates of hospitalization for heart failure (HHF) (2.7% vs. 4.1%; 35% relative risk reduction) and all-cause death (5.7% vs. 8.3%; 32% relative risk reduction; p-value 0.002).⁴ A 2017 real world claims analysis which studied HHF rates of T2D patients starting canagliflozin, dapagliflozin, or empagliflozin (53%, 42%, and 5% of patients, respectively) found a 39% risk reduction in HHF and 51% risk reduction in all-cause death versus other glucose reducing drugs.⁵ The overall safety profile of empagliflozin was found to be similar to that of placebo in the EMPA-REG OUTCOME trial.⁶

Though there are few studies on the cost effectiveness of empagliflozin, current literature suggests it is cost effective versus other antihyperglycemic agents (AHA). Real world analysis of the economic impacts of empagliflozin for patients with T2D demonstrates a per member per month (PMPM) reduction in all-cause healthcare costs of \$412 compared to other branded anti-hyperglycemic agents (DPP4-inhibitors, GLP1-agonists, other SGLT2-inhibitors, and

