9.2.2 Study population

Inclusion criteria:

- Prevalent metformin use + initiation of empagliflozin OR prevalent metformin use + initiation of a sulfonylurea
- ≥ 18 years of age at index date during study observation
- ≥1 inpatient and/or ≥ 2 outpatient claims denoting T2D diagnosis (in any position) in the 12 months prior to index date (Diagnosis codes available in the appendix Error! Reference source not found.)
- ≥1 inpatient and/or ≥2 outpatient claims denoting CVD (in any position) diagnosis in the 12 months prior to index date (Diagnosis codes available in the additional workbooks "ICD 9 Dx Codes.xlsx" and "ICD 10 Dx Codes.xlsx")
- ≥ 2 months post-index date
- ≥12 months of no exposure to T2D medications in the pre-index period (excluding metformin in both arms)
- ≥ 12 months of continuous enrollment prior to index date

Exclusion criteria:

- Diagnosis of Type 1 Diabetes, secondary, or gestational diabetes in the 12 months prior to index date (Diagnosis codes available in the additional workbooks "ICD 9 Dx Codes.xlsx" and "ICD 10 Dx Codes.xlsx"))
- Diagnosis of severe comorbidities including malignancy, end-stage renal disease, human immunodeficiency virus, Hepatitis C infection, or organ transplant in the 12 months prior to index date (Diagnosis codes available in the additional workbooks "ICD 9 Dx Codes.xlsx" and "ICD 10 Dx Codes.xlsx")
- Admission to nursing home in the 12 months prior to index date

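### The covariate list has no item for a prior heart-failure admission, so balance on the primary endpoint's own history is neither ensured nor checked

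*Protocol*

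**What the plan says.** **Outcome.** Protocol section 9.3.2.1 defines the primary outcome as "First hospitalization for congestive heart failure (HHF"), analysed first with the code in any position and then with principal or secondary position only. Section 9.1 starts observation at treatment initiation and ends it at the outcome, so the event is the first one after index.

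**Eligibility.** Section 9.2.2 requires CVD claims in the 12 months before index. The clinical exclusions are other forms of diabetes, the group beginning "Diagnosis of severe comorbidities including malignancy, end-stage renal disease, human immunodeficiency virus, Hepatitis C infection, or organ transplant in the 12 months", and "Admission to nursing home in the 12 months prior to index date". None concerns prior HF or a prior HF admission.

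**Covariates.** The section 9.3 table is presented as the full list of baseline characteristics, and the Abstract (Data analysis) builds the propensity score from the listed covariates. HF appears once, as "Heart failure; n". Comorbidities of this kind are "identified by occurrence of at least one ICD 9/10 for the respective condition in any position", with no inpatient/outpatient distinction. Admissions appear as "Hospitalization within prior 30 days; n" and "Hospitalization during prior 31-365 days; n", plus number of hospitalizations and hospital days, all without regard to cause. No item records an admission for HF.

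**Balance check.** Section 9.7.1 judges balance covariate by covariate and accepts standardized mean differences (SMDs) of up to 10%.

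**The concern.** A patient discharged after an HF admission shortly before index is at a different risk of HHF from a patient with an outpatient HF code and an unrelated admission. Both score yes on the HF item and yes on the recent-admission item. If one drug is chosen more often after an HF admission, the arms can agree on both items and still differ on their combination, and the primary hazard ratio absorbs the difference.

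Differential prescribing is plausible from the protocol's own background. Section 7 cites a published 35% relative reduction in HHF with empagliflozin, and the index window in section 9.1 runs from January 2015 to January 2020. Section 9.3 itself names confounding by indication as a concern.

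The list is finer elsewhere. Ischaemic history, which bears on the exploratory MACE outcome, is split into acute and old infarction, unstable and stable angina, other chronic disease and revascularization. The Abstract names hospitalized hypoglycaemia as a cause-specific baseline item. The history of the primary endpoint has one row.

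**Working it through.** The plan states no figure on this point. The only planning quantity used here is the hazard ratio of 0.65 (section 9.5), which agrees with the rates quoted there: 9.4/14.5 = 0.648. Everything else below is an assumption, because the documents do not give the residual imbalance or the hazard associated with a prior HF admission.

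**1. Balanced items, unbalanced combination.** Assume HF in 25% and a recent admission in 15% of each arm, so both SMDs are 0. Let the combination, taken here as an admission for HF, be 5% in the sulfonylurea arm and 8% in the empagliflozin arm. Assume relative hazards of 1 (neither), 4 (HF only), 1.5 (admission only) and 12 (HF admission).

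- Sulfonylurea: 0.65×1 + 0.20×4 + 0.10×1.5 + 0.05×12 = 2.200
- Empagliflozin: 0.68×1 + 0.17×4 + 0.07×1.5 + 0.08×12 = 2.425
- Bias factor: 2.425/2.200 = 1.10, so a true 0.65 is seen as 0.65×1.10 = 0.72.

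With 6 in place of 12 (exactly 4×1.5), the sums are 1.900 and 1.945. The factor is 1.02 and 0.65 is seen as 0.67. The bias comes only from the extra hazard of the combination beyond what the two separate items add up to.

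The SMD of the unlisted variable is (0.08 − 0.05)/√[(0.08×0.92 + 0.05×0.95)/2] = 0.12. That would fail the protocol's limit, but it is not computed because the variable is not listed.

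**2. Range of residual imbalance.** Treat prior HF admission as one omitted factor with prevalence p1 (empagliflozin) and p0 (sulfonylurea) after balancing, and relative hazard r. The bias factor is (1 + p1(r−1))/(1 + p0(r−1)).

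| p1 | p0 | r | SMD | Factor | 0.65 seen as |
|---|---|---|---|---|---|
| 4% | 3% | 3 | 0.05 | 1.08/1.06 = 1.02 | 0.66 |
| 5% | 3% | 5 | 0.10 | 1.20/1.12 = 1.07 | 0.70 |
| 10% | 5% | 5 | 0.19 | 1.40/1.20 = 1.17 | 0.76 |
| 2% | 3% | 5 | −0.06 | 1.08/1.12 = 0.96 | 0.63 |

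The sign follows the imbalance. The third row needs a large gap in a variable that is correlated with several checked items, so it is an outer case.

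**The case against.** The strongest reply is that the list already carries this history indirectly. A patient recently discharged after HF is flagged on the HF item and on admission within 30 days, and usually on number of admissions and hospital days. Emergency visits, loop diuretics, oedema, digoxin and cardiologist visits (within 30 days and at 31-365 days) would often separate that patient from a stable one admitted for something else. This stands. A reader might infer that patients started after an HF discharge are left unbalanced. The documents do not support that; they show only that balance on this history is not ensured and not checked. Nor does anything in them rank prior HF admission as the strongest predictor of HHF.

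A reader might also carry a large bias through to the main result. Suppose recent HF admission in 30% against 20% of HF patients with relative hazard 4: the factor is 1.90/1.60 = 1.19, and 0.65×1.19 = 0.77. That factor applies only within HF patients and assumes that the other items absorb nothing. If HF patients contributed 25% or 50% of events (assumed), the overall factor would be about 1 + 0.25×0.19 = 1.05 or 1 + 0.50×0.19 = 1.09, giving 0.68 or 0.71 before any adjustment through the other items.

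The indication change in section 7 ("In 2016 empagliflozin received a new indication for reducing cardiovascular death in patients with T2D and CVD") is weak evidence of selective prescribing. It concerns cardiovascular death in patients with CVD, and every patient here has CVD. Calendar quarter of entry is also a covariate. The published HHF result is the better ground.

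Two further inferences fail. The word first is not undefined, since section 9.1 makes it readable as first after index. And how to treat an admission in progress at index is an operational rule commonly left to the SAP.

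The exploratory instrumental-variable analysis (sections 9.3 and 9.7.2) addresses unmeasured confounding only if it proves feasible. It is no reason to leave out something the claims can measure.

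**Conclusion.** The point holds as a limited, inexpensive improvement to confounding control on the primary outcome. The protocol fixes its covariate list, and that list does not distinguish an admission for HF from an HF code plus an admission for another reason. The balance rule therefore cannot detect a residual difference on the endpoint's own history.

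Neither the size nor the direction of any bias can be derived from the documents. Under the assumptions shown, it is about 2% to 10% of the hazard ratio, somewhat more in the outer case, and it can run either way. It would be near zero if the existing items already balance the combination, or if HF admission adds no hazard beyond them. The conclusion does not depend on these magnitudes: it rests on the absence of the variable from a list presented as full, and on a balance check made one covariate at a time.

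**What to change.** Add two rows to the section 9.3 covariate table and to the propensity score: HF hospitalisation within the prior 30 days, and HF hospitalisation during the prior 31-365 days. Use the outcome's code list and the day split already used for all-cause admissions. Check both against the 10% SMD limit in section 9.7.1.

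The cost is two derived variables from claims already held, with no new data and no change to eligibility or follow-up.

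Optionally, report the HHF hazard ratio by baseline HF status as a descriptive sensitivity analysis. It will be imprecise. Section 9.5 shows 461 + 331 + 375 + 801 = 1,968 empagliflozin patients with any metformin supply before final cleaning; at 9.4 per 1,000 patient-years that is about 1,968×0.0094 = 18 to 19 events per year of average follow-up, before splitting.
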